9. STATISTICAL METHODS

9.1 SAMPLE SIZE ESTIMATION & JUSTIFICATION

The two primary outcome measures for this study are changes in Physical Health Composite (PHC) and Mental Health Composite (MHC) derived from the MSQOL-54. PHC and MHC are derived by combining scores of relevant subscales (Vickrey et al., 1995). For the proposed MSOC – RCT, sample sizes were calculated in order to detect a 5-point difference in the PHC and MHC scores (a minimum clinically meaningful change in these HRQOL measures, between the intervention and standard-care arms).

To further account for loss-to-follow-up from the study period, based upon MSOC - Feasibility results, we anticipated a 42% loss-to-follow-up between randomisation and follow-up at 12 months. It is likely

this level of loss-to-follow-up is an overestimate of what will be observed in the proposed MSOC – RCT due to redevelopment of the intervention based upon feasibility data, but this overestimate will account for participants in the standard-care course that request access to the MS Online Intervention course after unblinding at 12 months after participants undertake the MS Online Standard-care course.

Taking these factors into account, we estimate 1054 participants, 527 in each arm (1:1 allocation) with data at baseline and follow-up would give 80% power to detect a 5-point change in HRQOL across both PHC and MHC outcomes. This estimation of power is based on the mean PHC and MHC scores and their SD, which is the SD between groups at baseline.

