Primary Objectives:	
To determine whether participants adhering to lifestyle modification recommendations outlined in the MS Online intervention course have clinically significant increased health-related quality of life (HRQOL) in both domains of physical and mental health compared with participants following recommendations of the MS Online standard-care course. These outcomes will be examined in the short-term (6 and 12 months) and in the medium-term (2.5 years).
 
That is, we aim to determine whether participants in the Online intervention course following recommended lifestyle modifications have clinically significant and material increases in Physical Health Composite (PHC) and Mental Health Composite (MHC) scores, as derived from the validated tool designed to measure HRQOL in people with MS (MSQOL-54) compared with participants following recommendations of the Online standard-care course.

Secondary Objectives	
To determine whether participants following the lifestyle modification recommendations in the Online MS intervention course have improved depression, anxiety, fatigue, disability and self-efficacy in the short-term and medium-term compared with people following recommendations of the Online MS standard-care course.

Inclusion Criteria:	
Eligible participants must:
 
 1. Be able to read, write, and speak English; 2. Be 18 years old or over; 3. Have a confirmed diagnosis of relapsing-remitting MS by a neurologist preceding recruitment; 4. Be able to access the internet and be able to view sessions.
Exclusion Criteria:	
Exclusion criteria of participants include:
 
 1. Experiencing any serious co-morbid chronic illness or neurological illness/injury other than MS that would threaten regular participation or significantly affect the outcome measures in its own right, such as motor neurone disease or stroke, as determined by the study investigators; 2. Currently participating in another study or self-management program involving modification of lifestyle.
Number of Planned Participants:	
1054 participants, 527 in each arm at 1:1 allocation (intervention and standard-care arm)

Investigational product:	
Not applicable

Safety considerations:	
Participation in the study poses no physical risk to participants as the proposed RCT involves taking part in an Online MS

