8.3 REPLACEMENTS

Participants that withdraw from the study will not be replaced. (That is, participants that do not complete the MS Online course and all related follow-up in the form of completing MS Online questionnaires). The calculation of the sample size (Section 8.1) allows for a proportion of participants not complete to all components of the MS – RCT study (42% loss to follow-up) and still retain sufficient statistical power.

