9.2 POWER CALCULATIONS

Power calculations were estimated using the Bonferroni correction. The Bonferroni correction adjusts probability (p) values because of the increased risk of a type I error when making multiple statistical tests (in this instance, the increased risk of type I error for the multiple outcomes of PHC and MHC scores of HRQOL, as assessed by the MSQOL-54 questionnaire) (Osoba et al., 1998; Taphoorn, et al., 2005).

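### Section 9.1 attaches 80% power to 527 per arm with follow-up data, but 527 is the planned enrolment before an expected 42% loss; no power is given specifically for 2.5 years

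*Combined protocol and SAP*

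**What the plan says.** The synopsis lists as planned participants "1054 participants, 527 in each arm at 1:1 allocation". Section 9.1 sets the target as a 5-point between-arm difference in the PHC and MHC scores and states: "we anticipated a 42% loss-to-follow-up between randomisation and follow-up at 12 months". It calls this figure probably too high, but says the excess "will account for participants in the standard-care course that request access to the MS Online Intervention course after unblinding at 12 months". Having taken these factors into account, it concludes that "we estimate 1054 participants, 527 in each arm (1:1 allocation) with data at baseline and follow-up would give 80% power".

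Section 8.3 says "Participants that withdraw from the study will not be replaced", and that the sample size "allows for a proportion of participants not complete to all components of the MS" – RCT study, giving the allowance as "42% loss to follow-up) and still retain sufficient statistical power". It names no time point and counts completion of all follow-up questionnaires as part of completion.

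Section 9.2 says "Power calculations were estimated using the Bonferroni correction" for the two outcomes. Neither section gives the overall alpha, the sidedness or a value for the SD; Section 9.1 says only that the SD is the baseline one. Section 6.1, item IX, assesses the primary objective at 12 months and at 2.5 years.

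**The concern.** The same number is used in two incompatible ways. With 527 per arm enrolled, no replacement and 42% loss, 527 per arm cannot have follow-up data. Read literally, Section 9.1 promises 1054 participants with data, where the plan as a whole implies about 611 at 12 months. Which number the 80% belongs to matters a good deal, because power at the expected 12-month sample is very different under the two readings.

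The second issue is the period covered. Section 9.1 dates the 42% to 12 months, while Section 8.3 applies it to completion of the whole study. One of the two primary assessment times is 2.5 years, and no power or retention figure is tied to it. A reader could take the 80% to cover 2.5 years, which the plan does not show.

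**Working it through.** **Inputs from the documents.** 527 per arm (synopsis, 9.1); 42% loss (8.3, 9.1); difference of 5 points (9.1); power 80% (9.1); Bonferroni over two outcomes (9.2).

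**Assumed, because not stated.** Overall alpha 0.05 two-sided, so 0.025 per outcome; an SD as shown at each step; power read as power per outcome. Normal approximation, with z = 2.2414 for two-sided 0.025 and 0.8416 for 80% power.

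**1. Expected number with 12-month data.** 527 × 0.58 = 305.7, about 306 per arm. 1054 × 0.58 = 611 in total.

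**2. Can the plan's figure be reproduced?** Not without an SD. Solving SD = 5 × √(n/2) / (z_alpha + z_power) for 80% power gives:

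| Number with data per arm | SD, two-sided 0.025 | SD, two-sided 0.05 |
|---|---|---|
| 305.7 | 20.05 | 22.06 |
| 527 | 26.33 | 28.97 |

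Section 5.3 justifies 5 points partly by a half-SD rule, which would imply an SD of about 10. That gives 77 per arm, or 133 after inflation for 42% loss, so it does not reproduce 527 on either reading.

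**3. Reading A: 527 is already inflated for loss.** With assumed SD 20 and two-sided 0.025, n = 2 × ((2.2414 + 0.8416) × 20/5)² = 304.2, rounded up to 305; 305/0.58 = 526. With SD 22 and two-sided 0.05, n = 304 and 304/0.58 rounds up to 525. Both are close to 527. Using power = Φ(5 / (SD × √(2/n)) − 2.2414) with SD 20:
- n = 305.7: Φ(3.091 − 2.241) = 0.80
- n = 527: Φ(4.058 − 2.241) = 0.965

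On this reading, 527 per arm with data gives about 96%, not 80%.

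**4. Reading B: 527 is the evaluable number.** The implied SD is 26.33 at two-sided 0.025. At 305.7 per arm, power = Φ(2.348 − 2.241) = 0.54. At two-sided 0.05 (SD 28.97) it is 0.57. Having 527 per arm with data would then need 527/0.58 = 909 per arm enrolled (1818 in total).

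**5. How power moves with loss, on one basis.** Same formula, two-sided 0.025, n = 527 × (1 − loss). The losses other than 42% are illustrations.

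| Loss | n per arm | Power, SD 20 (A) | Power, SD 26.33 (B) |
|---|---|---|---|
| 35% | 342.6 | 85% | 60% |
| 42% | 305.7 | 80% | 54% |
| 50% | 263.5 | 73–74% | 48% |
| 60% | 210.8 | 63% | 39% |

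**6. Dependence on the analysis.** Section 9.3 names linear regression with adjustments and does not say whether baseline score is included. Take a raw SD of 20, 42% loss and an assumed baseline–follow-up correlation r of 0.4, 0.5 or 0.7. A change-score analysis, SD 20 × √(2(1 − r)) = 21.9, 20.0 or 15.5, gives 72%, 80% or 96%. A baseline-adjusted analysis, SD 20 × √(1 − r²) = 18.3, 17.3 or 14.3, gives 87%, 91% or 98%. So even the 12-month 80% depends on an unstated choice, and the two times must be compared on the same basis.

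**The case against.** The best defence is that this is loose wording in a sound calculation. Section 9.1 says the loss was taken into account, Section 8.3 says the sample size allows for it, and 305/0.58 = 526 sits almost exactly on 527. Section 9.1 also considers 42% an overestimate, and Section 8.3 can be read as stretching it over the whole study, including 2.5 years.

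Much of this stands. It makes reading A the likelier one. It does not prove it: the match depends on an SD and alpha that the documents do not supply. Nor does it remove the difference between Sections 8.3 and 9.1 on the period of the 42%, or provide a power figure for 2.5 years.

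Three stronger conclusions are tempting but not supported:
- **That the trial is underpowered at 12 months.** The 54% applies only if 527 was the evaluable number, which the text makes the less likely reading.
- **That power at 2.5 years falls below 80%.** It may be above or below, depending on loss, SD, baseline–follow-up correlation and analysis, none of which is fixed for that time.
- **That Sections 9.1 and 6.1 contradict each other on unblinding.** Section 6.1, item IX, makes early access for the standard-care arm conditional on an amendment, and defers notification of allocation to study completion only if there is none. The allowance in Section 9.1 can be read as provision for that contingency. The wording is unclear rather than contradictory.

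**Conclusion.** The point holds as a misstatement of the sample-size basis. As written, the power statement in Section 9.1 cannot be reconciled with the planned enrolment, the absence of replacement and the 42% loss: the expected number with 12-month data is about 306 per arm (611 in total), not 527. If 527 is the inflated number, 80% belongs to about 306 per arm and 527 with data would give about 96%. If 527 is the evaluable number, about 306 per arm gives about 54%. These powers assume two-sided 0.025 per outcome and SDs of about 20 and 26.3 respectively; the documents state neither.

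On 2.5 years the supportable claim is narrow. There is no power or retention figure specific to that time, and the period of the 42% is described differently in two sections. This should be fixed, but no shortfall in participants has been shown.

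**What to change.** - Check the original calculation and restate Section 9.1 with the randomised number (527 per arm) and the expected evaluable number at 12 months (about 306 per arm) shown separately, together with the SD, Bonferroni alpha and sidedness used.
- State 80% at about 306 per arm only if that calculation supports it. Otherwise give the power that about 306 per arm delivers.
- Reconcile Sections 8.3 and 9.1 on the period the 42% covers.
- Give power at 12 months and at 2.5 years on one common analysis and SD basis, over a range of loss that includes values below, at and above 42%.
- As a clarification only, align the reference in Section 9.1 to unblinding at 12 months with the conditional amendment in Section 6.1, item IX. Say whether standard-care participants who gain access count as lost or stay in the 2.5-year analysis; if they stay, a loss allowance does not cover any dilution of the between-arm difference.

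The cost is text and a check of existing working, with no extra participants. The downside is that the stated power may become less favourable than 80%.

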The Hospital Anxiety and Depression Scale (HADS) for the presence of and severity of anxiety and depressive symptoms. The HADS is commonly used for screening for anxiety and depression, as well as selecting and monitoring treatment and has been used to measure depression in MS (Zigmond & Snaith, 1983).

i. Patient-reported disability

The Patient-Determined Disease Steps (PDDS) is a self-reported measure of ambulatory disability. The PDDS is scored ordinally from 0 (normal) to 8 (bed bound) with detailed descriptors and definitions. It correlates well with the EDSS and moderately with the widely used Multiple Sclerosis Functional Composite and has excellent test-retest reliability. PDDS is considered a practical tool to use to assess changes in disability over time (Hohol, Orav, & Weiner, 1999). One step will be considered a clinically meaningful change in the PDDS.

j. Self-efficacy

Self-efficacy (the belief in one's ability to produce the effects or outcomes one wants) will be measured using the University of Washington Self-Efficacy (UWSE) survey, a psychometrically sound instrument that includes 6 items for measuring self-efficacy, validated in MS (Amtmann et al., 2012).

Primary intervention quantitative outcomes/endpoints:

The two primary outcome measures for this study are changes (improvements) from baseline in 1. Physical Health Composite (PHC) and 2. Mental Health Composite (MHC) derived from the MSQOL-54 in the short-term and medium-term. Differences of at least five points have previously been determined as the minimum clinically meaningful change in an HRQOL measure (Osoba, Rodrigues, Myles, Zee, & Pater, 1998; Taphoorn & Bottomley, 2005). Previous data suggests a difference of five points is achievable in a sample of people with MS (Hadgkiss, Jelinek, Taylor, et al., 2015).

Secondary intervention quantitative outcomes/endpoints:

Secondary outcomes include clinically relevant changes (improvements) in depression, anxiety fatigue, disability and self-efficacy in the short-term and medium-term.

QUALITATIVE OUTCOMES

A qualitative study using semi-structured interviews will be conducted within one month and 12 months after completing the MS Online course (the same group of people with MS will be interviewed at both time points).

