(PHC) and Mental Health Composite (MHC) scores derived from the MSQOL-54 for participants in the intervention and standard-care arm will be calculated in the intervention and standard-care arms.

We will consider amending the RCT protocol to allow participants in the standard-care arm access to the MS Online intervention course before the end of the study (ie before the 2.5-year follow-up) in the event:

- a) clinically significant increases in either the PHC and MHC scores of MSQOL-54 (≥ 5) (Osoba et al., 1998; Taphoorn & Bottomley, 2005) from baseline are found in participants in the intervention arm at the 12-month follow-up who are *adhering to lifestyle recommendations* of the Online Lifestyle modifications course, but
- b) clinically significant improvements in either PHC or MHC are not found in participants in the standard-care arm at the 12-month follow-up.

If clinically significant improvements in either the PHC and MHC scores of MSQOL-54 are not found between baseline and 12 months in participants in the intervention arm *adhering to lifestyle recommendations* of the MS Online intervention course, the RCT will continue to as described to the 2.5 year follow-up.

If there are no amendments to the study, all participants will be notified of the study arm they were allocated to at the completion of the study. All participants in the standard-care arm will be provided with a link to access the MS Online intervention course.

- X. Qualitative interviewing consisting of semi-structured interviews by trained qualitative interviewers will be conducted on a randomly selected subset of participants (approximately 15 participants from intervention and standard-care arms, respectively) will be performed within 1 month of and 12 months after completing the MS Online course.
- XI. During enrolment in the trial, participants in both arms of the RCT will be advised to continue with normal medical treatment with their existing neurologists and healthcare providers and to continue with their usual medications, as recommended by their physicians.

Intervention group (MS Online intervention course):

Structure of delivery

In a seven-module, seven-session, self-administered program, participants in the intervention arm would be presented with an integrated lifestyle modification program including information and

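### The primary objective asks for benefit in both PHC and MHC, but the power calculation uses Bonferroni, which suits a claim on either; the success rule and the meaning of the 80% must be fixed

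*Combined protocol and SAP*

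**What the plan says.** - **Synopsis, Primary Objectives:** the aim is "clinically significant increased health-related quality of life (HRQOL) in both domains of physical and mental health", judged against the standard-care course.
- **Section 5.3:** change in PHC and change in MHC are named as two primary outcome measures. No rule says how they combine into a trial conclusion.
- **Section 9.1:** "sample sizes were calculated in order to detect a 5-point difference in the PHC and MHC scores". With 1054 participants, 527 per arm, and an anticipated 42% loss by 12 months, the planned size "would give 80% power to detect a 5-point change in HRQOL across both PHC and MHC outcomes". An SD is said to have been used, but no value is given.
- **Section 9.2:** "Power calculations were estimated using the Bonferroni correction", the reason given being "the increased risk of type I error for the multiple outcomes of PHC and MHC scores of HRQOL". No numerical alpha or sidedness is stated.
- **Section 9.3:** the analysis methods contain no multiplicity rule and no test level.
- **Section 6.1, item IX:** a possible amendment at 12 months is tied to "clinically significant increases in either the PHC and MHC scores of MSQOL-54".

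**The concern.** Two different claims are mixed. If the trial succeeds only when both composites are positive, testing each at 5% already keeps the chance of a false overall claim at or below 5%, so Bonferroni gives power away for nothing. If success on either composite is enough, some adjustment is needed, but then the synopsis objective is worded wrongly and describing the 80% as covering both composites is misleading. At least one of the three statements (synopsis, 9.1, 9.2) therefore needs correcting.

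The practical risk is a mixed result. If PHC is positive and MHC is not, the document can be cited for success (two outcomes, Bonferroni) or for failure (both domains required). That choice would be made on the primary endpoint after the data are known. A further question is whether 80% is the chance of showing each effect or the chance of showing both.

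**Working it through.** **Inputs from section 9.1:** difference 5 points on each composite; 527 per arm; 42% loss; power 80%.

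**Assumed, because not stated:** two-sided overall alpha 0.05, hence 0.025 per composite under Bonferroni; 527 is the number enrolled; the same SD for PHC and MHC; a true difference of 5 on both; correlation r between the two test statistics of 0 to 0.8.

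**1. Can the stated 80% be reproduced?** Not directly, because there is no SD. Solving for it instead:

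- Evaluable per arm: 527 × 0.58 = 305.7.
- For 80% per composite at 0.025: SD = 5 × √(305.7/2) / (2.2414 + 0.8416) = 61.81/3.083 = 20.05.
- Forward check with SD 20: n = 2 × 20² × 3.083² / 5² = 304.2, so 305 per arm, and 305/0.58 = 526. This is close to 527.

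The fit does not identify the inputs. SD 22 at 0.05 without Bonferroni gives 304 per arm, and 304/0.58 = 525. If 527 were the number with data, the SD for 80% per composite at 0.025 would be 26.3.

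**2. Power under each rule, if 80% is per composite at 0.025.** The expected test statistic is 3.083. Per-composite power at 0.05 is Φ(3.083 − 1.960) = 86.9%. Joint probabilities come from the bivariate normal distribution. For at least one, the figure is 0.80 + 0.80 − P(both). For both under Holm, it is 2 × P(one passes 0.025 and the other passes 0.05) − P(both pass 0.025); at r = 0 this is 2 × 0.800 × 0.869 − 0.640 = 0.751.

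| Rule | r = 0 | r = 0.5 | r = 0.8 |
|---|---|---|---|
| Both, each at 0.025 (Bonferroni kept) | 64.0% | 68.7% | 72.9% |
| Both, each at 0.05 | 75.6% | 78.6% | 81.6% |
| At least one, at 0.025 | 96.0% | 91.3% | 87.1% |
| Both significant under Holm | 75.1% | 77.8% | 80.4% |

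**3. Sensitivity to the unstated inputs.**

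- If 80% is already joint power with Bonferroni kept and 305.7 evaluable per arm, the implied SD is 17.7 (r = 0) to 18.7 (r = 0.8), and there is no shortfall.
- If SD is 20 and 527 per arm are evaluable, power for both at 0.025 each is 93–95%.
- If SD is 10, as the half-SD remark in section 5.3 would suggest for a 5-point difference, joint power exceeds 99.9%.
- If one composite has SD 20 and the other 17 (assumed), power for both at 0.025 each is 74–79%.

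**The case against.** The tempting reading is that the trial really has only 64–73% power for its primary objective. The documents do not support that as fact. The SD behind the figure was obtained by assuming that 80% is per composite at 0.025, which is the point in question. Section 9.1 can be read as already claiming joint power, and its wording can also be read as 527 per arm with data. The figure further combines a both-must-succeed rule with Bonferroni, a pairing no one would choose deliberately. Under the two coherent rules, the same assumptions give 76–82% or 87–96%. This objection stands, and the 64–73% is usable only as a labelled conditional.

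A reader might also infer from section 6.1 that success on either composite is the rule. That item concerns when to consider opening the intervention course to control participants, using change from baseline within each arm, and among adherers in the intervention arm. It is not a between-arm success criterion and settles nothing here.

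Finally, an objective naming both domains is not a formal decision rule, and two separately tested primary outcomes with 80% power each is a coherent design. Bonferroni would then be valid. But the plan does not say that this is the design, the objective would still need rewording, and the mixed-result ambiguity would remain.

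**Conclusion.** The inconsistency is in the text and needs no assumption: an objective requiring both composites, a power statement covering both, and a correction suited to either. The plan lacks a success rule and does not say whether 80% is per composite or joint.

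The size of any power loss cannot be fixed from the documents. If 80% is per composite at two-sided 0.025, keeping Bonferroni while requiring both costs about 9 to 12 percentage points against testing each at 0.05 (72.9% against 81.6% at r = 0.8; 64.0% against 75.6% at r = 0). An SD near 20 with 42% loss is consistent with that assumption but does not prove it.

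**What to change.** Before any unblinded data are seen, choose one rule and make the synopsis and sections 9.1, 9.2 and 9.3 agree. Section 9.3 needs a sentence giving the test level and the multiplicity rule.

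**(a) Both composites must succeed.** Test PHC and MHC each at two-sided 5% without Bonferroni, and claim primary success only if both are significant. Restate power as joint power, using the sponsor's actual planning SDs and an assumed correlation, not the back-calculated values above. Cost: one positive composite is no longer a primary success.

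**(b) Either composite suffices.** Reword the objective to PHC or MHC, state that 80% is per composite if the sponsor's calculation confirms it, and replace Bonferroni with Holm. Holm keeps the same family-wise error and never has less power; under the assumptions above, the chance of showing both rises from 64–73% to 75–80%. Cost: the trial gives up the claim that its primary objective requires benefit in both domains.

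Under either option, state the SD for each composite, the numerical alpha and sidedness, and whether 527 per arm is enrolled or evaluable. These are changes of wording and test level, with no change to data collection. The sample size needs another look only if the sponsor's own inputs show joint power to be inadequate under (a).

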The 12-item multidimensional Scale of Perceived Social Support (MSPSS) will be used to measure participants' social interaction and satisfaction with social support (Zimet, Dahlem, Zimet, & Farley, 1988). Higher score of MSPSS indicates higher quality of social support.

Health outcomes of participants will be assessed at baseline and 6, 12 and 30 months after completion of the respective Online MS course. Health outcomes measured include:

f. Mental and physical quality of life (qol)

The MSQOL-54 will be used to assess a spectrum of HRQOL outcomes. In particular, the two primary outcome measures for this study will be change in Physical Health Composite (PHC) and Mental Health Composite (MHC) derived from the MSQOL-54. PHC and MHC are derived by combining scores of relevant subscales (Vickrey, Hays, Harooni, Myers, & Ellison, 1995). Although minimal clinically important differences have not been established for the MSQOL-54 composite scores, differences of at least five points have previously been determined as the minimum clinically meaningful change in an HRQOL measure (Osoba et al., 1998; Taphoorn, et al., 2005). This is based on recommendations that a difference

equivalent to half the standard deviation be universally considered an important magnitude for all HRQOL tools (Norman, Sloan, & Wyrwich, 2003). The MSQOL-54 has been psychometrically validated since 1995, used online and also translated into many different languages.

g. Fatigue

Clinically significant fatigue will be measured by the 9-item Fatigue Severity Scale (FSS) (Krupp, LaRocca, Muir-Nash, & Steinberg, 1989). The FSS has good internal consistency, stability, and sensitivity to change over time (Amato et al., 2001; Smedal et al., 2011). A mean score ≥ 4 has been suggested as a cut-off to indicate clinically significant fatigue and is widely used for people with MS (Lerdal, Celius, & Moum, 2003; Marrie et al., 2005; Smedal et al., 2011). A meaningful change on the FSS has been reported demonstrated to be a change of ≥ 1.9 points in people with MS (Learmonth et al., 2013) and so here a change in mean score of 1.9 points or more will be considered clinically meaningful.

h. Anxiety and depression

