The complete patient-reported questionnaire with approximately 150 questions has been found to take approximately 60 minutes to complete. Participants will be able to login and complete this questionnaire over time. The participants will be requested to complete this questionnaire on four separate occasions (baseline, 6 months, 12 months and 2.5 years) and due to previous studies that we have performed within the Neuroepidemiology Unit utilising questionnaires of a similar length over 7.5 years ((Marck et al., 2018; Weiland et al., 2018), we do not believe the questionnaire will create an unacceptable burden on participants.

Quantitative data analysis:

We will measure adherence to lifestyle modification recommendations in people with MS enrolled in the MS Online intervention and the MS Online standard-care arm (control) using validated patient-reported questionnaires.

We will examine and compare clinical and health outcomes of depression, anxiety, fatigue, disability, self-efficacy and quality of life in people with MS in the short-term (6 months and 12 months) and medium-term (2.5 years) in people enrolled in the MS Online Intervention course arm and people enrolled in the MS Online standard-care course arm.

Statistical analyses will enable us to examine whether a causal relationship exists between lifestyle factors and clinical and health outcomes in people with MS. These analyses are anticipated to be completed within 6-12 months of collecting data for short-term and long-term analyses, respectively.

Qualitative data:

Qualitative data will comprise edited transcripts of recordings from semi-structured interviews from 15 randomly selected participants from the intervention arm and the standard-care arm carried out within one month of completing the MS Online course and 12 months after completing the MS Online course (the same people will be interviewed at both time points).

Interviews will be digitally recorded and transcribed by voice recognition software. Data will be stored in a re-identifiable format and encrypted files will be securely stored as described in Section 10.

Qualitative data collection feasibility:

The qualitative component of the MSOC – RCT is similar to the qualitative component of the MSOC – Feasibility study we performed. This interviewing technique was found to be both effective and participants reported positive feedback following interviews.

Qualitative data analysis:

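### Section 9.1 computes power from the baseline SD of PHC and MHC, but the primary outcomes are changes from baseline, so the 80% is not tied to the SD the analysis will face

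*Combined protocol and SAP*

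**What the plan says.** Section 5.3 (Outcome Measures) gives the primary outcomes as "changes (improvements) from baseline in 1. Physical Health Composite (PHC) and 2. Mental Health Composite (MHC"). Section 9.1 repeats that they are changes in the two composites.

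Section 9.1 then says that "sample sizes were calculated in order to detect a 5-point difference in the PHC and MHC scores" between the arms. It anticipates 42% loss by 12 months and states 80% power with 527 per arm. Its variance input is described in one sentence: "This estimation of power is based on the mean PHC and MHC scores and their SD, which is the SD between groups at baseline". No numerical SD, SD of change or correlation between baseline and follow-up appears in the documents.

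Section 9.2 adds a Bonferroni correction for the two composites, without giving the nominal alpha or whether tests are one- or two-sided. Section 9.3 plans linear regression for quality of life with adjustment for confounders. It does not say whether the dependent variable is the change or the follow-up score, or whether the baseline score is a covariate.

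**The concern.** A power figure holds only for the analysis whose SD went into it. The SD of a change depends on how strongly follow-up tracks baseline, and the baseline SD carries no information about that. If the comparison is of raw changes, the same 1054 participants could give power well below or well above 80%. Nothing in the plan lets a reader tell which.

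The description of the SD as one between groups adds a smaller problem. The quantity a two-arm comparison needs is the spread between people within an arm. This may be only loose wording, but with no number printed it cannot be checked.

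**Working it through.** **Inputs.** From section 9.1: difference 5 points, 527 per arm, 80% power, 42% loss by 12 months, so 527 × 0.58 = 306 evaluable per arm. From section 9.2: Bonferroni over two outcomes. Assumed, because not stated: overall two-sided alpha 0.05, so 0.025 per outcome; 80% power for each outcome separately; normal approximation.

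**Can the 80% be reproduced?** Not from stated inputs, because the SD is missing. It can only be back-solved. With z-values 2.2414 and 0.8416 (sum 3.0830), SD = 5 / (3.0830 × √(2/n)):

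- n = 306 evaluable per arm: SD = 20.1
- n = 527 evaluable per arm: SD = 26.3

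Both readings are possible, because section 9.1 describes "we estimate 1054 participants, 527 in each arm (1:1 allocation) with data at baseline and follow-up" just after allowing for loss. An SD of 20 needs 305 per arm, and 305 / 0.58 = 526, close to 527. That makes about 20 a plausible origin, but it remains an assumption. The half-SD remark in section 5.3 ("equivalent to half the standard deviation be universally considered an important magnitude for all HRQOL tools") would put the SD at 10. That needs 77 per arm, or 77 / 0.58 = 133 enrolled, and does not give 527.

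**Power for the SD that applies.** Let f be the ratio of the SD used in the analysis to the baseline SD. Taking 80% as right at f = 1,

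power = Φ(3.0830 / f − 2.2414).

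The sample size cancels, so the result is the same for 306 and 527 evaluable per arm. With equal variances at both times:

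- unadjusted change score: f = √(2(1 − r))
- follow-up score or change with baseline as a covariate: f = √(1 − r²)

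For example, at r = 0.3 the change score has f = √1.4 = 1.183, and Φ(3.0830/1.183 − 2.2414) = Φ(0.364) = 64%.

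| r | Power, unadjusted change | Power, baseline as covariate |
|---|---|---|
| 0 | 48% | 80% |
| 0.3 | 64% | 84% |
| 0.4 | 72% | 87% |
| 0.5 | 80% | 91% |
| 0.6 | 89% | 95% |
| 0.7 | 96% | 98% |

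The 80% at r = 0.5 in the middle column is built in by the calibration and confirms nothing. What the column shows is sensitivity: power stays within 2 points of 80% only for r between about 0.48 and 0.52.

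**Numbers needed.** For 80% power on an unadjusted change score, the evaluable number per arm is n × 2(1 − r). Starting from 306, that is 429 at r = 0.3, 368 at 0.4, 245 at 0.6 and 184 at 0.7. Starting from 527, it is 738, 633, 422 and 317.

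**Unequal variances.** If the follow-up SD is k times the baseline SD, the variance of change is SD²(1 + k² − 2rk). This equals SD² when r = k/2, so the break-even correlation is 0.45 at k = 0.9 and 0.55 at k = 1.1. The covariate floor also needs k²(1 − r²) ≤ 1, which holds at every r when k ≤ 1.

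**The case against.** The strongest reply is that the baseline SD may be a reasonable or even cautious input. Section 9.1 speaks of a difference in scores between arms, and for an unadjusted comparison of follow-up scores the score SD is the right kind of quantity. Under randomisation the expected difference between arms is the same for follow-up scores and for changes, so the 5 points carry over. If the regression in section 9.3 includes the baseline score, then with equal variances power is at least 80% at every r.

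This stands as far as it goes, and it rules out one tempting reading. A reader might infer that the 80% is right only at r = 0.5, or that the trial is underpowered. The first needs an unadjusted change-score analysis and equal variances, and the documents state neither. The second needs, in addition, a low correlation that the documents do not give.

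The reply does not rescue the text, however. Both section 5.3 and section 9.1 name change as the outcome, and section 9.3 does not name baseline as a covariate. The favourable reading has to be supplied by the reader.

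Two further inferences also go beyond the documents. One is that a single SD was used for both composites; section 9.1 does not say so. The other is that the 2.5-year comparison is the weak one. Section 6.1 does list 2.5 years for the primary objective, but section 9.1 gives a loss figure only to 12 months and claims no separate power at 2.5 years. No correlation is given for either time.

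**Conclusion.** The point holds as a mismatch between the stated outcome and the variance behind the stated power. On an unadjusted change score with equal variances, the 80% becomes anything from about 64% to 96% as r goes from 0.3 to 0.7. With baseline as a covariate it becomes 84% to 98% over the same range.

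These figures assume a two-sided alpha of 0.025 per outcome and that 80% is correct at the baseline SD. They do not depend on whether 306 or 527 per arm are evaluable. The SDs of about 20 and 26 are back-solved and are not facts about the trial. The error can go either way, and nothing here shows that 1054 is too few. What needs correcting is the power statement and its inputs.

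**What to change.** - **Section 9.3:** state that the primary linear regression for PHC and for MHC includes the baseline score as a covariate.
- **Section 9.1:** recompute the power with the matching residual SD, or with the SD of change if no baseline adjustment is made. Print the SD for each composite, the alpha per outcome and a stated range of r, for example 0.3 to 0.7. Give the result for the 12-month comparison, the time for which a loss figure exists.
- **Section 9.1, wording:** replace the reference to an SD between groups with the between-person SD within an arm.
- Keep N at 1054.

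Section 6.1 mentions the unit's earlier long-running questionnaire studies, though only to argue that the burden is acceptable. If they hold repeated MSQOL-54 scores they could supply r; the documents do not say that they do, so a range is enough.

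The cost is a short recalculation and revised wording. The stated power may change, and if no baseline adjustment is made it may fall below 80% at the lower correlations.
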